## List of Abbreviations

ABFM	American Board of Family Medicine
AHRQ	Agency for Healthcare Research and Quality
APA	American Psychiatric Association
CFR	Code of Federal Regulations
CHRT	Concise Health Risk Tracking
EHR	Electronic health record
EMR	Electronic medical record
FDA	U.S. Food and Drug Administration
FIBSER	Frequency, Intensity, and Burden of Side Effects Ratings
GCP	Good Clinical Practice
GPP	Good Pharmacovigilance Practices
HAM-D	Hamilton Depression Score
HIPAA	Health Insurance Portability and Accountability Act of 1996
ICH	International Committee on Harmonization
ICMJE	International Committee of Medical Journal Editors
IRB	Institutional review board
ISPE	International Society for Pharmacoepidemiology
MDD	Major Depressive Disorder
MIPS	Merit-based Incentive Payment System
OMF	Outcome Measures Framework
PHQ-9	Patient Health Questionnaire – 9
PRO	Patient Reported Outcome
PsychPRO	Psychiatric Patient Registry Online
SAP	Statistical analysis plan

## 1. Background

A patient registry is defined as “an organized system that uses observational study methods to collect uniform data (clinical and other) to evaluate specified outcomes for a population defined by a particular disease, condition, or exposure and that serves one or more pre-determined scientific, clinical, or policy purposes.” Patient registries fulfill different purposes for a wide range of stakeholders, as documented in the publication, *Registries for Evaluating Patient Outcomes: A User’s Guide*. Given their myriad purposes, it is unsurprising that a large number of registries exist – over 5,000 according to the [ClinicalTrials.gov](http://ClinicalTrials.gov).

Together, these registries represent an enormous investment in research infrastructure and a tremendous data resource that could be used to address new research questions in a timely and efficient manner. Yet, linkage and comparisons of data across registries to address research questions is challenging, if not impossible, because of variation in both the concepts and definitions of the outcome measures used in registries within the same clinical area. Even when the outcome concept is the same (e.g., remission in depression), registries may define the measure differently (e.g., using the Hamilton Depression Rating Scale [HAM-D] vs. the Patient Health Questionnaire-9 [PHQ-9]) because very few standardized definitions exist. This limits the potential of registries to support new research and serve as a foundation for learning health systems and national health data infrastructure. This also introduces inefficiency in registry data collection. Many organizations, such as health systems, participate in multiple registries, but data must be captured differently for each registry. Incorporation of key data elements within electronic health record (EHR) systems would reduce the burden of registry data entry, but, for many organizations, the cost of incorporating each registry’s unique data elements within the EHR system is too high.

To address these issues, patient registries must implement standardized outcome measures that can be captured consistently as part of routine clinical practice across care settings and seamlessly transferred into different registries. These outcome measures also must be useful in routine clinical practice for informing treatment decision and monitoring patients over time. The Agency for Healthcare Research and Quality (AHRQ) has supported the development of the Outcomes Measures Framework (OMF), a conceptual model for classifying outcomes that are relevant to patients and providers across most conditions. Under this OMF project, minimum sets of standardized outcome measures suitable for use in registries and clinical practice were developed in five clinical areas, including depression.

While registries, clinicians, and other stakeholders expressed enthusiasm about standardized outcome measures, they identified several barriers to implementation in registries and in clinical practice during workgroup meetings for the previous project. First, stakeholders noted the difficulty of working with different EHRs to extract data for patient registries. Registry sites often use EHRs from different vendors; even when sites use the same vendor (e.g., Epic), they often have customized implementations that make extraction of data in a standardized manner difficult. In reviewing the standardized measures, stakeholders also expressed concerns about the burden on patients and clinicians of capturing patient reported outcomes (PROs) on a regular basis, particularly for long-term follow-up. Lastly, stakeholders noted the potential for disruptions to clinical care if clinicians are asked to document additional information in

structured fields (as opposed to notes). Many stakeholders emphasized the need for pilot testing to demonstrate the feasibility of implementing the harmonized measures and to show the value of the harmonized measures – both in terms of reduced burden of data entry and the ability to generate data of sufficient quality for registry-based research.

The proposed project will implement the harmonized outcome measures in a manner that addresses these barriers, using depression as a test case. Major depressive disorder (MDD) is a common mental disorder that affects an estimated 16.2 million adults and 3.1 million adolescents in the United States. Characterized by changes in mood, cognitive function, and/or physical function that persist for two or more weeks, MDD can reduce quality of life substantially, impair function at home, work, school, and in social settings, and result in increased mortality due to suicide. MDD also is a major cause of disability, with an economic burden of approximately \$210.5 billion per year in the United States.

Despite the burden of MDD and the availability of treatment, the condition is often undiagnosed and untreated. In 2016, the U.S. Preventive Services Task Force recommended screening for depression in the general adult population, including pregnant and postpartum women, and in adolescents. While routine screening is intended to improve diagnosis and treatment of MDD, many questions remain, such as about the comparative effectiveness of different treatment approaches, the incidence of adverse events, when to add medications for patients who do not respond to an initial course of treatment, how and why depression recurs, and how to classify and treat treatment-resistant depression. MDD patients also may receive care from different providers, such as primary care physicians, psychologists, and psychiatrists. Care coordination is important for improving patient outcomes but can be difficult to achieve even within the same health system.

Patient registries capture a wealth of data on depression treatment patterns and outcomes in the United States and could serve as the foundation for a national research infrastructure to address these and other research questions. Yet, as documented in the prior project, existing registries use different outcome measures (e.g., remission as defined by the PHQ-9 vs. HAM-D) and capture data at different timepoints. Similarly, data are not captured consistently across practice settings in routine clinical practice.

## **2. Rationale**

Depression registries offer an excellent opportunity to demonstrate the feasibility and value of implementing the harmonized outcome measures. Existing registries, such as the American Psychiatric Association's (APA) Psychiatric Patient Registry Online (PsychPRO) and the American Board of Family Medicine's (ABFM) PRIME Registry, already capture some of the necessary data for the harmonized measures for quality reporting purposes, although at different timepoints; capture of these measures and the additional measures at consistent intervals will enable the registries to generate more robust data suitable for research purposes. A feasibility study will show that it is technically feasible for registries to collect the data elements necessary to calculate the harmonized outcome measures and to pool the de-identified data for research purposes.

A pilot study is necessary to show that is possible to capture the standardized outcome measures in the clinical workflow, without overburdening clinicians or patients; to provide the measure information back to clinicians to help inform patient care; and to submit the data to different patient registries.

### **3. Objectives**

The purpose of this pilot study is to demonstrate feasibility and value of collecting a subset of the harmonized outcomes measures for MDD in the primary care and mental health setting.

Objectives:

[figure not shown]
- Demonstrate that it is technically and operationally feasible to use an open-source app to extract the selected outcome measures, including PHQ-9 information, from existing clinical systems and provide the calculated measure results in the clinician’s workflow.
- Assess burden of capturing the measures from patients (PHQ-9) and clinicians and value of providing the measure results.

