#### 4.6 Data Collection

No data will be collected solely for the purposes of this study. All data elements will be collected from information routinely recorded in the EHR or other relevant data sources (e.g., a standalone PRO platform). No visits or examinations, laboratory tests or procedures are mandated as part of this study. In addition, the app will be implemented locally, meaning that no data will leave the health system IT systems. The app will have the ability to transmit data externally (e.g., to a patient registry), but this feature will not be activated during the pilot study.

The capture of PROs, specifically the PHQ-9, at regular intervals is critical for implementation of the depression outcome measures. Practices participating in this pilot project will capture the PROs at regular intervals (including outside of clinical visits with reminders sent to patients) using a standalone PRO system implemented within the health system. This is done as part of routine clinical care for patients with depression, and data captured in this manner are used to calculate quality measures for submission to the Centers for Medicare and Medicaid Services under the Merit-based Incentive Payment System (MIPS).

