## 5. Qualitative Assessment

No formal statistical analysis is planned for this pilot study, and no sample size calculations were done. We anticipate that approximately 50 patients enrolled at five practices will be sufficient to address the objectives of this pilot study.

The purpose of this analysis is to assess the feasibility and value of the open-source app. Clinicians and other personnel (e.g., IT staff) at participating practices will be asked to complete a brief web-based survey at the conclusion of the data collection period to provide feedback on the app. The survey will contain approximately 20 questions assessing three domains: usability of the app, burden of using the app, and overall value of the app for informing patient care and improving engagement with patients. Results of the survey will be summarized in a final study report and in a publication. No patient data will be included in the assessment phase.

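### The burden half of objective 2 is only partly measured: the staff survey asks about using the app, while the PHQ-9 is captured in a separate system

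*Protocol*

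**What the plan says.** Protocol section 3 lists two objectives. The first is technical and operational feasibility of the app. The second is to "Assess burden of capturing the measures from patients (PHQ-9) and clinicians and value of providing the measure results". Section 2 gives the background to the second: a pilot is needed to show that the measures can be captured "without overburdening clinicians or patients".

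Section 5 describes the only assessment. Its aim is given as "The purpose of this analysis is to assess the feasibility and value of the open-source app". On who is asked, it says "Clinicians and other personnel (e.g., IT staff) at participating practices will be asked to complete a brief web-based survey", once data collection has ended. The survey has about 20 questions in three domains: "usability of the app, burden of using the app, and overall value of the app". The section closes with "No patient data will be included in the assessment phase".

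Section 4.6 explains that practices collect the PHQ-9 at regular intervals as routine care, "using a standalone PRO system implemented within the health system", and that nothing is collected only for the study.

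**The concern.** The objective names the burden of capturing the measures. The survey asks about the burden of using the app. These are different quantities, because the app does not capture the PHQ-9: patients complete it in another system, partly away from visits and after reminders. A clinician or IT worker can find the app effortless while patients find repeated questionnaires tiresome, or the reverse.

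At stake is what the final report can say. A statement that regular PHQ-9 capture did not overburden patients would have no data behind it. A statement about clinicians' capture workload would rest on answers to questions framed around a different tool. The burden of collecting patient-reported outcomes is one of the barriers that section 1 says stakeholders raised and the project is meant to address, so readers will look for an answer.

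**Working it through.** No arithmetic applies. The protocol gives no sample-size derivation, target or threshold for burden. The check is whether each part of objective 2 has a respondent, an instrument or a data element anywhere in the protocol.

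**Step 1. Split objective 2 into parts.** (a) Burden of PHQ-9 capture as it concerns patients; (b) burden of capture as it concerns clinicians; (c) value of the displayed results.

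**Step 2. List every possible source of data.**

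- Section 4.1: the app connects to the EHR, combines EHR and patient-reported data, calculates the measures and returns the results. It does not administer the PHQ-9.
- Section 4.4, outcome table: suicide death, remission, response, recurrence, adverse events, suicidal ideation and behavior. None concerns the burden of data capture. The FIBSER entry rates the burden of treatment side effects, which is something else.
- Section 4.6: the PHQ-9 comes from a separate system. Reminders exist, but no count of them is planned as a study result.
- Section 4.6.1, data elements: patient characteristics, disease, treatments, outcomes. There is no completion rate, completion time, reminder count or staff time.
- Section 5: a staff survey with the domains "usability of the app, burden of using the app, and overall value of the app for informing patient care" and patient engagement.

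**Step 3. Match parts to sources.**

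| Part of objective 2 | Respondent | Instrument or data element | Covered? |
|---|---|---|---|
| (a) Patients, PHQ-9 capture | None; patients are not surveyed | None; section 5 excludes patient data | No |
| (b) Clinicians, capture | Clinicians | Nearest is the app-burden domain | Proxy at most |
| (c) Value of results | Clinicians and other staff | Value domain | Yes |

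**Step 4. Check for an indirect route to (a).** Counts of PHQ-9s due and completed would exist in the routine system, but the section 5 sentence "No patient data will be included in the assessment phase" keeps them out of the assessment as it is worded.

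**The case against.** Several points on the other side have weight.

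*The objective is ambiguous.* The word *from* may name patients and clinicians as the sources of the data, with the burden falling on the practice. Staff would then be the right respondents. This reading is possible, although sections 1 and 2 both speak of burden on patients. Even so, the stated domain concerns the app and not capture, so the mismatch narrows but does not vanish.

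*The survey items are not shown.* Some of the roughly 20 questions could touch on capture. This stands for clinicians. A reader might infer that clinician capture burden is wholly unmeasured; the protocol does not support that, since only domain labels are given. It does not help patients, who are neither asked nor counted.

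*Section 2 is rationale.* A reader might take it as a promise of evidence on patient burden. The same sentence also mentions submitting data to registries, which section 4.6 says will be switched off in this pilot. It explains why a pilot is wanted and does not list what this study delivers. The point therefore rests on section 3.

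*PHQ-9 capture is routine care.* Section 4.6 says so, which means that the study adds no PHQ-9 burden and no patient is exposed to a study burden that goes unwatched. This lowers the stakes but leaves the objective unanswered.

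*A separate analysis plan might fill the gap.* Section 5 itself fixes the respondents, the domains and the exclusion of patient data. An analysis plan could not analyse what is not collected.

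**Conclusion.** The point holds in limited form. Patient burden of PHQ-9 capture has no measurement under the plan as written; clinician capture burden has at most a proxy; the value of the displayed results is covered, and the feasibility objective is not affected. In size, this is one part of a three-part objective with nothing behind it and one part with indirect support.

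This rests on two assumptions: that objective 2 includes burden borne by patients, which sections 1 and 2 favor but section 3 does not state outright; and that the figures missing from the available text add no burden instrument.

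The point should be corrected, but it is not a fatal fault. In an observational feasibility pilot with no formal analysis, harm arises only if the report concludes something about burden that the survey could not show.

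**What to change.** Change section 5 as follows.

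1. Split the survey's burden domain in two: the burden of capturing the PHQ-9 and other measure data, including how staff perceive the burden on patients, and the burden of using the app. Report clinicians apart from IT staff.
2. Have the health system report aggregate counts from the PRO system: PHQ-9s due, reminders sent, and PHQ-9s completed in the 6-month and 12-month windows. Label these as a feasibility indicator and an indirect proxy for patient burden. Amend the sentence excluding patient data so that aggregate counts are allowed while no patient-level data leave the health system, which keeps to sections 6.1 and 8.4.
3. If these are not adopted, narrow objective 2 to staff burden and the value of the displayed results, and draw no conclusion that patients were not overburdened.

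The cost is a few reworded items in a survey of about 20 questions and one aggregate query, with no new patient contact. The limitation is that completion counts do not measure burden directly: a missed questionnaire may reflect a missed visit, disengagement or recovery. Staff perception is likewise second-hand. The report should say so.

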### **4. Study Design**

#### **4.1 Study Description**

The study is a longitudinal, observational pilot study that will assess the utility and value displaying the harmonized outcomes data to clinicians in the clinical workflow using an open-source, SMART on FHIR app. The app will connect with the site EHR, aggregate EHR and PRO data, calculate the outcome measure results, and return the results to the EHR so that they are viewable within the clinician workflow. Baseline data on patient characteristics, treatments, and symptoms will be combined with longitudinal data on outcomes during the study timeframe (see Figure 1). All data will be collected from institution electronic medical records (EMRs), PRO portals, and other existing data sources, as needed.

#### **Figure 1. Study Design**

## 4.2 Study Population

The study will collect data on approximately 50 patients from a total of five practices within the same health system.

### 4.2.1 Inclusion Criteria

The following criteria must be met in order to be enrolled in the study:

- Patients age 18 and older
- Diagnosis of major depression or dysthymia
- Willing and able to provide informed consent

### 4.2.2 Exclusion Criteria

There are no exclusion criteria for this study.

### 4.2.3 Study Enrollment

Both specialist (mental health) and general practice sites within the participating health system will be targeted for recruitment. Sites with the ability to implement a SMART on FHIR app will be prioritized. Selection criteria and basic site information (e.g., site size, site type) will be collected via a site qualification survey.

All eligible patients identified during the determined enrollment period at the site will be enrolled.

### 4.2.4 Patient Withdrawal

Patients may withdraw from the study for any reason at any time.

### 4.3 Exposure Definition and Measures

This is an observational pilot study focused on technical and operational feasibility in this patient population. This protocol does not recommend the use of any specific treatments, and all assessments are captured as part of routine clinical care.

### 4.4 Outcome Definitions and Measures

Outcome Measure	Definition
Death from suicide	
Patient age 18 or older with a diagnosis of major depression or dysthymia who died from suicide, reported in 12-month intervals.
 
This should be captured where feasible; however, this information may not be recorded accurately or available to all providers.

Improvement in Depressive Symptoms: Remission	
Patient age 18 or older with a diagnosis of major depression or dysthymia and an initial PHQ-9 score > 9 who demonstrates remission defined as a PHQ-9 score less than 5.
 
Timeframe for measurement: Baseline, 6 months post baseline (+/- 60 days), 12 months post baseline (+/- 60 days)

Improvement in Depressive Symptoms: Response	
Patient age 18 or older with a diagnosis of major depression or dysthymia and an initial PHQ-9 score > 9 who demonstrates a response to treatment defined as a PHQ-9 score that is reduced by 50% or greater from the initial PHQ-9 score.
 
Timeframe for measurement: Baseline, 6 months post baseline (+/- 60 days), 12 months post baseline (+/- 60 days)

Worsening in Depressive Symptoms: Recurrence	
Patient age 18 or older with a diagnosis of major depression or dysthymia and an initial PHQ-9 > 9 who demonstrates remission (defined as a PHQ-9 score < 5) of at least two months' duration and subsequently experiences a recurrence of a depressive episode, defined as a PHQ-9 score > 9 OR hospitalization for depression or suicidality.
 
Timeframe for measurement: Baseline, 6 months post baseline (+/- 60 days), 12 months post baseline (+/- 60 days)

Adverse Events	
Depression treatment-related adverse events, captured using the Frequency, Intensity, and Burden of Side Effects Ratings (FIBSER) scale and extracted from data routinely recorded in the EMR.
 
Timeframe for measurement: Baseline, 6 months post baseline (+/- 60 days), 12 months post baseline (+/- 60 days)


Suicide Ideation and Behavior
	
Selection of ‘several days’, ‘more than half the days’ or ‘nearly every day’ option on PHQ-9 item 9 (“Thoughts that you would be better off dead or of hurting yourself in some way”) and/or documentation of nonfatal suicide attempts/suicide attempt behaviors, planning/preparatory acts, or active suicidal ideation extracted from data routinely recorded in the EMR.
 
Timeframe for measurement: Baseline, 6 months post baseline (+/- 60 days), 12 months post baseline (+/- 60 days)
 
Note, supplemental assessments of suicide ideation and behavior should be completed for patients who screen positive for suicide ideation on the PHQ-9 or when a clinician has concerns about suicidality. Supplemental assessments should be completed using an appropriate, brief, validated instrument, such as the Concise Health Risk Tracking (CHRT) scale.

--------------------------------------	--

